Some patients may leave the hospital with the midline in place for additional intravenous therapies. If the patient is discharged with the midline, the research team will discuss the infusion plan with the care management team. Patients will also be provided detailed contact information of the Vascular Access Team (standard practice) at the time of hospital discharge in case any questions or complications arise. If the patient develops any concerning signs or symptoms for the venous thromboembolism, the Vascular Access Team will instruct the patient to return to the outpatient clinic for an evaluation with a member of the Vascular Access Team, schedule an urgent appointment with the medical doctor, or check into the Emergency Department for further evaluation. The research team will document imaging results from these encounters. All patients will receive follow-up phone call assessments by the research team. Patient disposition options include: discharge home/residence or to a skilled nursing facility or transfer to another hospital. If the patient is discharged home, infusion and catheter care occurs via home care or at an infusion center. For patients discharged to a skilled nursing facility, catheter care and infusion is managed by nursing staff at these centers. These patients will continue to be followed in the posthospital setting, specifically to assess for the complication of thrombosis. The research staff will follow-up via telephone call with staff managing the infusion within 48-72 hours of discharge and weekly including the last day of therapy to inquire about the VAD site and function of the catheter and document any complications/results to radiographic imaging. Once the rapy is completed and the catheter is removed, the research team will follow up with the patient or designated legally authorized representative/next of kin via phone to inquire about the access site at 30 days post

line removal. All patients will receive the 30 day follow-up phone contact. Patients will specifically be asked if they developed redness, swelling, or pain at the catheter insertion site and had radiographic evaluation for a blood clot or pulmonary embolism. If the patient has a concern, the research team will forward the concern to [name] and [name] for further evaluation per routine.

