SVT and DVT rates will be calculated based on upper extremity proven diagnosis of SVT and/or DVT in symptomatic cases. Researchers will review all study subject records in EPIC, the electronic medical records system, and screen enrolled subject data for all upper extremity venous Doppler examinations. Radiology interpretations will be reviewed for findings consistent with CR-UEVT. This review will occur thirty days post patient discharge. Symptoms and rationale for imaging will be documented. This information will be obtained by reviewing the order/provider documentation in EPIC. If the patient is diagnosed with thrombophlebitis, the location of the thrombus will also be documented.

Infection rate will be tracked using confirmed catheter-related blood stream infection data from the surveillance team within the epidemiology department. The team utilizes the CDC definition of laboratory-confirmed blood-stream infection (LCBSI). See Appendix A for LCBSI definitions and pathway for diagnosis.

The medication administration record will be queried for all medications given through each catheter. Vesicants that are generally given via central line or considered caustic to the vessel will be noted in both groups. Number of doses will be recorded. See Appendix B for full list of non-neoplastic vesicants. We will also collect data on patients that received alteplase for occlusion. We will specifically evaluate the relationship of alteplase use and how it relates to catheter-related thrombosis, catheter-related bloodstream infection, and functionality of catheter.

Sample Size and Statistical Analysis

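### For patients discharged with the midline, the only stated systematic Doppler search of the record is done before planned thrombosis follow-up ends

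*Combined protocol and SAP*

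**What the plan says.** Under Objective, Specific Aim 1 counts symptomatic superficial and deep thromboses confirmed by Doppler. To find them, the Follow-up Assessment section has researchers screen EPIC for every upper extremity Doppler in enrolled subjects and read the radiology reports. It dates that step from discharge: "This review will occur thirty days post patient discharge". No later or repeated screen is stated.

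The same section runs follow-up on a different clock. "Some patients may leave the hospital with the midline in place for additional intravenous therapies". These patients are followed after hospital "specifically to assess for the complication of thrombosis". The final contact is made "via phone to inquire about the access site at 30 days post" line removal, and every patient is to receive it.

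The section also describes other ways of learning about an event:

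- Staff managing the infusion are called 48-72 hours after discharge, then weekly and on the last day of therapy, to "document any complications/results to radiographic imaging".
- Patients are given the Vascular Access Team's contact details, and those with worrying symptoms are directed to care. "The research team will document imaging results from these encounters".
- At the 30-day call, patients are asked about local symptoms and whether they "had radiographic evaluation for a blood clot or pulmonary embolism". If there is a concern, "the research team will forward the concern to" named clinicians for routine evaluation.

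**The concern.** The search is timed from discharge and the end of follow-up from line removal. The two dates agree only if the line comes out on the day of discharge. For a patient who leaves with the line, the last part of planned follow-up falls after the one search that does not depend on anyone reporting anything.

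This affects the primary outcome, which requires Doppler confirmation. A thrombosis imaged after the search date could be missed. It could also be mentioned by phone and stay unverified, because no step is written for obtaining the report of imaging first mentioned in the final call.

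Planned events are few, so each one carries weight. Reading the 11% reduction in the Sample Size paragraph as percentage points, the two arms together are planned to yield:

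- 106 × (0.12 + 0.01) = 13.8 to 106 × (0.15 + 0.04) = 20.1 events with 106 per group;
- 13.8 × 0.8 = 11.0 to 20.1 × 0.8 = 16.1 events if the 20% buffer is lost.

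These counts give scale only. They do not estimate what the timing would lose.

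**Working it through.** The plan gives no figure to reproduce here; the check is date arithmetic.

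**Inputs.** The search is at discharge + 30 days and the final contact at removal + 30 days (both Follow-up Assessment). Median dwell is 10 days (Sample Size, a planning value for Aim 3). The documents do not give t, the days the line stays in after discharge, or the share of patients discharged with a line. All t values below, and all dwell times other than 10 days, are assumptions.

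**Step 1: the gap.** Let discharge be day 0 and removal day t.

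- Search: day 30.
- End of planned follow-up: day t + 30.
- Follow-up days after the search: (t + 30) − 30 = t.
- Post-removal days the search can see: max(0, 30 − t).

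| t (assumed) | Search | End of follow-up | Days after search | Post-removal days searched, of 30 |
|---|---|---|---|---|
| 3 | day 30 | day 33 | 3 | 27 |
| 7 | day 30 | day 37 | 7 | 23 |
| 10 | day 30 | day 40 | 10 | 20 |
| 14 | day 30 | day 44 | 14 | 16 |
| 28 | day 30 | day 58 | 28 | 2 |

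At t of 30 or more, the search sees no post-removal days. At t = 0 the two dates coincide. If the line is removed before discharge, the search falls later than 30 days after removal, so there is no gap.

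**Step 2: the share of planned follow-up.** With total dwell D, planned follow-up from insertion is D + 30 days, and the share after the search is t/(D + 30). The line is placed before discharge, so t is less than D and the share is below D/(D + 30).

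- D = 10: t = 3 gives 3/40 = 7.5%; t = 7 gives 7/40 = 17.5%; upper bound 10/40 = 25%.
- D = 14: upper bound 14/44 = 31.8%.
- D = 21: upper bound 21/51 = 41.2%.
- D = 30: upper bound 30/60 = 50%.

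The bounds are approached only when discharge follows insertion almost at once.

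**Step 3: what covers the t days.** While the line is in place, the calls to infusion staff record imaging. They stop on the last day of therapy. After removal, and once the search date has passed, two routes remain: contact with the Vascular Access Team, which the patient must start, and one call that relies on self- or proxy-report.

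**The case against.** The strongest reply is that little is likely to slip through. The outcome is symptomatic, so a late case has a reason to seek care. Patients have a number to ring, imaging from encounters arranged that way is recorded with no end date, and the final call asks all patients about symptoms and clot imaging. To be lost, an event must be late, imaged outside those encounters, and either not reported at the call or reported and not pursued. For t below 30, the search covers the whole dwell and part of the month after removal, so the uncovered days are the tail of that month. Nothing says that event counting stops at the search or that staff would not reopen a chart. The rule is the same in both arms.

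Most of this stands, and it limits the weight of the point. It does not remove the mismatch. The remaining routes after removal need the patient to make contact, be reached or recall correctly, and a patient who fails on all of these has no later chart search as a backstop. Requiring a proven diagnosis keeps unverified reports out of the count, but it also means that a true late event counts only if someone retrieves the report, and that step is not written.

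Two further objections are fair. Imaging done outside EPIC is invisible at any search date, so retrieving it is a separate remedy. And a search date does not itself define which Doppler dates count as events.

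**Conclusion.** The mismatch is certain: for every patient discharged with the midline, the search comes t days before planned thrombosis follow-up ends. Patients whose line is out by discharge are unaffected.

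The consequence is much less certain. The sizes above are shares of days under assumed values of t, and the 10-day dwell is a planning median, not a figure for patients sent home with a line. The number of events missed is probably small and cannot be computed from the documents. No direction of bias is shown. Because the gap equals post-discharge dwell, the unscreened days could differ between arms if dwell did, but that is only a possibility. The change is worth making because it concerns ascertainment of the primary outcome and costs little.

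**What to change.** In Follow-up Assessment, date the EPIC Doppler search at the later of 30 days after discharge and 30 days after removal of the index midline, and carry it out at or after the 30-day call. The uncovered interval then becomes zero for every t. No search moves earlier, so no Doppler found under the present rule is lost.

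Add a sentence requiring that the report of any imaging mentioned by phone or done elsewhere be obtained before the event is counted. Apply both steps identically in the two arms.

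The cost is protocol wording, a chart review t days later for patients discharged with a line, and some record retrieval. Sample size, alpha and planned power do not change.

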TITLE: Randomized Comparative Evaluation of Midline Catheters for Thrombophlebitis

NCT03725293

Approval date: 04/30/2019

Protocol and Statistical Analysis Plan

Randomized Comparative Evaluation of Midline Catheters for thrombophlebitis

Introduction

Establishment and maintenance of intravenous (IV) access are core processes in providing medical care for hospitalized patients. For patients requiring extended duration of therapy, the peripherally inserted central catheter (PICC) Team is often consulted for patient assessment and vascular access device placement at many hospitals. PICCs are central catheters that are placed via peripheral vein under ultrasound guidance and may be used for patients with difficult venous access for long-term central or peripheral infusion therapies as well as central venous pressure monitoring in a critical care setting. Although PICCs provide a great option for some patients, these catheters have known complications including catheter- related bloodstream infection, catheter-related venous thrombosis, malfunction, and high cost. Midline catheters represent a potentially attractive alternative to PICCs for peripheral infusions. These catheters have been utilized since the mid 1980s but fell out of favor in the early 1990s due to reports of acute life threatening hypersensitivity reactions. In the last few years, midlines have made a resurgence in the market and are FDA cleared for use in patients requiring intermediate to longterm infusion therapies. Advances in midline catheters offer the potential for reduced complications. As midlines have increased in popularity and new midlines have been introduced into the market, it is necessary to better understand complication profiles of various midline catheters, as it is likely that all catheters are not created equal. Specifically, the incidence of symptomatic catheter-related thrombosis is of interest. While this complication has been researched extensively for PICCs with an incidence of 1.8 – 8.4%, data on this complication for midlines represents a gap in the literature. One recent publication cited a 4.5% rate of all symptomatic catheter-related venous thrombosis (combined superficial venous thrombosis (SVT) and deep venous thrombosis (DVT)) in patients with midline catheters. Another study found a catheterrelated venous thrombosis rate of 2.5% when limiting measured outcomes to occurrence of DVT. Internal retrospective

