data at our institution suggests a rate closer to 12-15% for all symptomatic catheterrelated venous thrombosis (SVT and DVT). Some midline catheters are coated to provide protection against catheter-related venous thrombosis and/or catheterrelated bloodstream infection. The theoretical benefit(s) of these catheters need further validation in human subjects.

Objective

We aim to understand the difference in symptomatic catheter-related upper extremity venous thrombosis (CR-UEVT) comparing the Teleflex Arrowg+ard Blue Advance 4.5 F single lumen midline catheter to the AngioDynamics BioFlo 4 F single lumen midline catheter. Both catheters are inserted using a modified seldinger technique (MST). The AngioDynamics product has Endexo technology with claims of reduced platelet aggregation and favorable thrombus accumulation profile. The Teleflex catheter is a chlorhexidine coated device that claims to be both antithrombogenic and antimicrobial.

Specific Aim 1: To compare incidence of symptomatic CR-UEVT between the AngioDynamics Bioflo midline catheter and the Teleflex Arrowg+ard Blue Advance midline catheter.

For Aim 1, we will measure incidence of all symptomatic CR-UEVT inclusive of superficial thrombophlebitis (SVT) and deep venous thrombosis (DVT) confirmed by upper extremity venous doppler evaluation, to assess whether Arrowg+ard midline catheters offer a reduction in the incidence of symptomatic CR-UEVT.

Specific Aim 2: To compare incidence of catheter-related bloodstream infection between the AngioDynamics BioFlo midline catheter to the Teleflex Arrowg+ard Blue Advance midline catheter.

For Aim 2, we will identify cases of infection per the laboratory confirmed bloodstream infection criteria published by the Center for Disease Control (CDC), to assess whether Arrowg+ard Blue Advanced midline catheters offer reduction in catheter-related bloodstream infection.

Alternatively, for Aim 1 and Aim 2, to further examine the incidence of overall complications in the light of the differing catheter dwell times, catheter days data (including multiple insertions of midline catheters per patient in the study period) will be analyzed.

Specific Aim 3: To compare catheter survival rate data between the AngioDynamics BioFlo midline catheter and the Teleflex Arrowg+ard Blue Advance midline catheter.

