Sample Size: For this randomly allocated, two group experiment, the primary outcome was complication profile in terms of thrombophlebitis. Under Aim 1, based on the preliminary analysis using approximately 13 months of data at William Beaumont Hospital, it suggested the incidence of thrombosis between 12-15% from 1,200 insertions of AngioDynamics BioFlo midline catheters with the diagnosis of symptomatic thrombosis. We established a one-sided Fisher's exact twoproportions test with a type I error $\alpha = 0.05$. In terms of results from previous study [1], sample size was designed to have a power of 80% for detecting a 11% lower in the incidence of thrombosis using Teleflex Arrowg+ard Blue Advanced midline catheters. Based on these criteria, 212 participants will be randomly allocated to 2 study groups (106 per group). This sample size included a 20% buffer to account for potential sample loss. For Aim 3, this sample size has a power of 0.85 to detect a hazard ratio of 1.5 for failure of functionality association with AngioDynamics BioFlo midline catheters, based on a log rank test with a 0.05 one-sided significant level and median time of midline catheter introduction into a vein of 10 days [1]. All above calculations were made using the power software PASS 16.

Statistical Analysis: For Aim 1 and Aim 2, we will use descriptive statistics (frequency, percent) to summarize the incidence of complication profile in terms of thrombosis and infection between these two groups. For Aim 1, a logistic regression model will be built to examine the association between midline catheters and the presence of thrombosis, adjusting for participant characteristics. The odds ratio (OR) associated midline catheters on thrombosis will be estimated. For Aim 2, we will further create cases of bloodstream infection per 1000 catheter-days,

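### Does the 11-point effect behind the sample size lack a traceable source and lose its 80% power in the upper part of the plan's control range?

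*Combined protocol and SAP*

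**What the plan says.** The sample size paragraph (Sample Size and Statistical Analysis) sizes Aim 1 with a one-sided Fisher's exact test at a type I error of 0.05. For BioFlo, the internal data are summarised thus: "it suggested the incidence of thrombosis between 12-15% from 1,200 insertions". The effect is introduced by "In terms of results from previous study [1], sample size was designed to have a power of 80% for detecting a 11% lower". The result is 212 participants, 106 per group, and "This sample size included a 20% buffer to account for potential sample loss".

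The Introduction gives two published midline rates. One is a "4.5% rate of all symptomatic catheter-related venous thrombosis (combined superficial venous thrombosis (SVT) and deep venous thrombosis (DVT)) in patients with midline catheters"; the other is a "rate of 2.5% when limiting measured outcomes to occurrence of DVT". It then says that internal "data at our institution suggests a rate closer to 12-15% for all symptomatic catheterrelated venous thrombosis (SVT and DVT"). Under Specific Aim 1 the endpoint is the combined one: "we will measure incidence of all symptomatic CR-UEVT inclusive of superficial thrombophlebitis (SVT) and deep venous thrombosis (DVT").

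The sample size paragraph states neither a single control rate nor a Teleflex target rate, and it does not give the evaluable number per group that the buffer is meant to protect.

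**The concern.** A two-proportion calculation needs two rates, and the plan prints only a range for one of them and a difference. The difference is attributed to a cited study. The reference list as shown carries no numbers, so which study is [1] has to be inferred. The same paragraph takes a midline dwell time from [1], which points to one of the two listed midline studies, and the Introduction quotes two published midline rates. Subtracting the combined published rate (4.5%) from 12-15% never gives 11 points. Subtracting the other rate (2.5%) gives exactly 11 at the middle of the range, but that rate counts deep thrombosis only, while Aim 1 and the 12-15% count superficial and deep thrombosis together.

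If the 11 points came from mismatched endpoints, the trial would be sized on too large an effect. A null Aim 1 result would then be read against an 80% that the design did not have. A second worry is that, once the buffer is used up, 80% does not hold over the whole control range that the plan itself quotes.

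**Working it through.** **Inputs.** All come from the sample size paragraph except the two published rates (Introduction): one-sided Fisher's exact test, alpha 0.05; 106 per group; 20% buffer; control rate 12-15%; reduction of 11; published rates 4.5% (combined) and 2.5% (deep only).

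**Absolute or relative.** The text says 11% without saying which. A relative 11% reduction would need roughly 5,500 to 7,100 per group, so only 11 percentage points fits 106.

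**Evaluable number.** The buffer can be read in two ways: 106 × 0.8 = 84.8, about 85; or 106 / 1.2 = 88.3, about 88.

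**Method.** Exact power = sum over all pairs (x, y) of Bin(x; n, p_control) × Bin(y; n, p_target), counting pairs whose one-sided hypergeometric tail is at most 0.05.

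**Reproducing 106 per group.** Smallest n per group with power of at least 80% for an 11-point drop, then inflated:

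| Control vs target | n evaluable | n / 0.8 | n × 1.2 |
|---|---|---|---|
| 12% vs 1% | 69 | 86.3 | 82.8 |
| 13.5% vs 2.5% | 83 | 103.8 | 99.6 |
| 13.9% vs 2.9% | 88 | 110.0 | 105.6 |
| 14% vs 3% | 89 | 111.3 | 106.8 |
| 15% vs 4% | 99 | 123.8 | 118.8 |

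The stated 106 corresponds to a control rate of about 13.5-14%, inside the quoted range. At 13.9% vs 2.9% the n × 1.2 convention rounds up to exactly 106.

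**Power at 11 points, by evaluable number per group:**

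| Control vs target | 85 | 88 | 106 (no loss) |
|---|---|---|---|
| 12% vs 1% | 89.9% | 91.2% | 95.1% |
| 13.5% vs 2.5% | 81.1% | 82.6% | 88.9% |
| 14% vs 3% | 78.3% | 79.8% | 87.0% |
| 15% vs 4% | 73.3% | 75.0% | 83.5% |

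Power crosses 80% at a control rate of 13.7% with 85, 14.0% with 88 and 16.0% with 106. The last lies above the plan's range. At 15% vs 4%, 99 evaluable per group gives 80.3%, so 106 − 99 = 7 per group, or 7/106 = 6.6%, can be lost before power falls below 80%.

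**Source of the 11 points.** Against 4.5%: 12 − 4.5 = 7.5 and 15 − 4.5 = 10.5. Against 2.5%: 12 − 2.5 = 9.5, 13.5 − 2.5 = 11.0 and 15 − 2.5 = 12.5. The documents contain no combined-endpoint pair that gives 11, but they also do not say that the 11 was obtained by this subtraction.

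**The case for a change.** The strongest case for acting is that the sizing of the primary comparison should be reproducible, and here a reader must guess a control rate to recover 212. The implied target of 2.5-3% for combined thrombosis has no source in the documents. The one natural pair that gives exactly 11 mixes a combined rate with a deep-only rate. Rounding 15 − 4.5 = 10.5 up to 11 does not help, because power at a 15% control rate after the full loss is 68-70% against 4.5% and 73-75% against 4%. If the Teleflex rate were 4.5%, power after the full loss would be 45-70% across the range. One or two sentences would settle all this.

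Part of this stands. The design rates and the evaluable number are not printed, and the attribution cannot be traced from the documents. The rest does not carry through:

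- The cited study is not available here, and it may report other rates or subgroups. The attribution is unverified, which is different from wrong. The missing reference numbers may also be a loss in text extraction, so they carry no weight.
- The plan claims 80% power for a design scenario. It does not claim it at every rate in a range that describes retrospective data.
- The 45-70% figures need a 4.5% Teleflex target. The plan never adopts one, and the 4.5% is a general midline rate.
- The 73-75% figures need the top of the range and loss of the entire buffer together. Full loss is not a given: the Follow-up Assessment section has every enrolled subject's record screened for upper extremity Doppler examinations, and a patient discharged with the catheter is still followed.

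**Conclusion.** The concern does not call for a change. The 106 per group and the 80% agree with each other for an 11-point drop at a control rate in the middle of the plan's own range: 81.1% or 82.6% after the full 20% loss, depending on how the buffer is read. With no loss, the claim holds at every rate from 12% to 15% (83.5-95.1%). The shortfall at the upper end is about 5 to 7 points of power (80 − 75.0 = 5.0; 80 − 73.3 = 6.7) and arises only when two unfavourable conditions coincide.

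What remains is missing detail: the control rate, the target rate and its source, and the evaluable number. A statistician reading the result can recover the likely design point, as above, and would in any case judge a null finding by the confidence interval and the observed control rate. Printing the rates would leave enrolment, data collection, analysis and conclusion as they are.

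This rests on reading 11% as percentage points, on the Fisher test that the plan names for sizing (the power figures do not describe the adjusted logistic model), and on the buffer meaning either 85 or 88 evaluable per group. It does not establish that the cited study supports 11 points; the documents cannot settle that either way.

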For Aim 3, an improved survival of Arrowg+ard Blue Advanced midline catheters will be evaluated by functionality of catheter for intravenous therapy prior to patient discharge. The event is failure of functionality identified during follow-up assessment during hospitalization. Duration of dwell and functional failure of the catheter will be employed to estimate catheter survival.

Study Design

We propose a prospective single-site, parallel, two-arm, randomized investigation to assess catheter-related symptomatic UEVT, catheter-related bloodstream infection, and functionality of two single lumen midline catheters: AngioDynamics BioFlo 4 F and Teleflex Arrowg+ard Blue Advance 4.5 F. The research protocol was approved by the Institutional Review Board of Beaumont Research Institute. Written informed consent will be obtained from all participants.

All inpatients 18 years of age and older that require midline catheter placement by the bedside vascular access team will be eligible participants. Patients will be excluded if: Do not meet inclusion criteria 2. Multiple lumens required 3. Alternative diameter of catheter used 4. If already enrolled once prior 5. Withdraw voluntarily from the study 6. Are receiving oral, intravenous, or subcutaneous treatment dose anticoagulation (prophylaxis with anticoagulant is permissible).

Research staff of Beaumont Health Institute will allocate two midline catheters to eligible participants according to a pre-generated randomized list at a 1:1 ratio in block randomization to AngioDynamics BioFlo or Teleflex Arrowg+ard Blue Advanced midline catheters. Participant enrollment will take place from November 2018 until patient recruitment is complete. Demographic and health-related information will be obtained from electronic medical records during enrolled period at William Beaumont Hospital.

Practitioner Participation/Training

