travel > 6 hours within past 4 weeks 8. Inflammatory Conditions (IBD, SLE) 9. Immobilization >72 hours 10. Other. Indication for catheter placement will also be recorded: 1. DIVA 2. Antibiotics 3. Incompatible Medications 4. Other

Follow-up Assessment

Investigators will perform a follow-up assessment on all catheters within 24 hours of insertion and then daily for the life of the VAD. Generally all follow-up evaluations will occur between 8 am and 10 am. At each follow-up interval, the researcher will document the time of evaluation and assessment of functionality as well as review the patient chart for signs and symptoms of catheter-related bloodstream infection and document the presence of localized site infection. A catheter is functional if the investigator is able to withdraw 3-5 ml of blood or if the VAD flushes without resistance with 5 mL of saline. Even if the line is actively infusing upon evaluation, the investigator will stop the infusion and assess for functionality by drawing blood and flushing. Data specific to blood sampling will be collected daily. If the catheter was identified to have failed during follow-up assessment the date and time of failure and the reason for failure will be documented. If the catheter failed or was removed prior to the follow-up assessment then the VAD failure time and the assessment of failure and reason for line removal will be obtained through chart review. For all failed catheters, re-insertion attempt data will be tracked through the medical record in the nursing section for venous lines and need for reinsertion of the midline or escalation to a PICC, or CVC will be noted. If the patient is discharged prior to the time of follow-up assessment then the time of discharge will be documented and the VAD will be presumed functional until time of discharge unless otherwise noted in the chart.

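### The 0.85 power claimed for Aim 3 holds only if about 175 of 212 catheters (83%) fail, and the plan neither states nor supports that failure share

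*Combined protocol and SAP*

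**What the plan says.** The Sample Size paragraph (Sample Size and Statistical Analysis) first sets 212 participants, 106 per group, for the thrombosis comparison in Aim 1. It adds: "This sample size included a 20% buffer to account for potential sample loss". It then says of Aim 3 that "this sample size has a power of 0.85 to detect a hazard ratio of 1.5 for failure of functionality", with BioFlo as the arm at higher hazard. The stated basis is a one-sided 0.05 log-rank test and a "median time of midline catheter introduction into a vein of 10 days", cited to an earlier study. No number of failures, failure proportion or censoring rate is given for Aim 3, and no length of observation in days.

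Other sections fix what counts as a failure and how lines leave observation:

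- **Objective, Specific Aim 3.** Catheter survival is "evaluated by functionality of catheter for intravenous therapy prior to patient discharge". The definition follows: "The event is failure of functionality identified during follow-up assessment during hospitalization". Time in place and failure are named as two quantities: "Duration of dwell and functional failure of the catheter will be employed to estimate catheter survival".
- **Follow-up Assessment, in hospital.** Each catheter is checked every day while it is in. If a patient goes home before that day's check, "the VAD will be presumed functional until time of discharge unless otherwise noted in the chart".
- **Follow-up Assessment, after discharge.** "Some patients may leave the hospital with the midline in place for additional intravenous therapies". Lines are taken out once therapy is complete.

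**The concern.** A log-rank test gains information only when a catheter fails. Quoting power for 212 catheters therefore implies a number of failures, and here that number is large. The one input that could justify it, the 10-day median, is worded as time in the vein. A line that is removed while still working ends its time in the vein without failing, so a median dwell does not fix how many catheters will fail. The in-hospital event definition and the planned removals also let working lines leave without an event.

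At stake is the plan's only statement of how well Aim 3 is powered. A reader who meets a non-significant Aim 3 result could set it against a planned power of 0.85 without being able to see that the figure depends on about five catheters in six failing.

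**Working it through.** **Inputs from the plan.** Hazard ratio 1.5, one-sided alpha 0.05, power 0.85, 212 participants, 20% buffer and 10-day median (Sample Size); 1:1 allocation (Study Design). Constants: z(0.95) = 1.645, z(0.85) = 1.036, ln 1.5 = 0.4055.

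**1. Failures needed for the stated power.**

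- Schoenfeld: D = 4 × (1.645 + 1.036)² / 0.4055² = 174.9, and 174.9 / 212 = 82.5%.
- Freedman: D = ((1.5 + 1) / (1.5 − 1))² × (1.645 + 1.036)² = 179.7, and 179.7 / 212 = 84.8%.
- Any power that rounds to 0.85 (0.845 to 0.855) needs 172 to 178 failures. Power of 0.80 needs 150 (71% of 212).

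**2. Reproducing the 0.85.** Power = Φ(0.4055 × √D / 2 − 1.645).

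| Route | Failures | Power |
|---|---|---|
| All 212 fail | 212 | 0.904 |
| 212 / 1.2 = about 176 remain, all fail | 176 | 0.852 |
| 212 × 0.8 = about 170 remain, all fail | 170 | 0.841 |
| 212 catheters, failure medians 10 v 15 days, each watched 32 days | 176.3 | 0.852 |

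The figure is therefore reachable. If the buffer were lost without contributing any failure, 174.9 / 176 = 99% of the remainder would have to fail on one reading of 20%. On the other reading (170 left), the ceiling is 0.84.

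**3. Power by assumed failure share.** The documents give no share, so these are assumptions.

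| Share of 212 | Failures | Power |
|---|---|---|
| 70% | 148.4 | 0.80 |
| 50% | 106.0 | 0.67 |
| 30% | 63.6 | 0.49 |

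**4. If 10 days were a true failure median in one arm.** The arm is not stated. With a hazard ratio of 1.5, the medians are either 10 (BioFlo) v 15 days, or 6.7 v 10 (Teleflex). Assume exponential failure, every catheter watched for T days and no other censoring. Expected failures = 106 × [(1 − 2^(−T/m₁)) + (1 − 2^(−T/m₂))].

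| T (assumed) | 10 v 15: failures, power | 6.7 v 10: failures, power |
|---|---|---|
| 10 days | 92.2, 0.62 | 121.5, 0.72 |
| 14 days | 116.3, 0.71 | 147.1, 0.79 |
| 20 days | 143.4, 0.78 | 172.2, 0.845 |
| 30 days | 172.2, 0.845 | 194.1, 0.88 |

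For 174.9 failures, T must be 31.3 days (10 v 15) or 20.9 days (6.7 v 10).

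**5. The same medians with random censoring.** With exponential censoring of median c, expected failures = 106 × [c/(c + m₁) + c/(c + m₂)]. At c = 10 days this gives 95.4 failures and power 0.63 (10 v 15), or 116.6 and 0.71 (6.7 v 10). Reaching 174.9 needs c of about 58.6 or 39.0 days.

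Simulated one-sided log-rank tests (106 per arm, 6,000 runs per setting) agree closely: for example 0.624 and 0.728 at T = 10, and 0.625 and 0.710 at c = 10.

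**The case against.** The strongest reply is that no figure in the documents shows power below 0.85. Every lower value above comes from an assumed failure share, observation time or censoring rate. That stands, and it limits the conclusion to what the 0.85 depends on.

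The other arguments carry different weight:

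- **The 10-day input may have been a failure median.** It is cited to a source not available here, and naming dwell and failure separately may simply describe the time variable and the event indicator of a survival analysis. A reader might infer that the wrong median was used. The documents do not show how it was entered, so only the ambiguity is established. Even as a failure median, it yields 175 failures only with the long observation in steps 4 and 5.
- **The plan does describe an observation period.** Catheters are checked daily for as long as they are in, so follow-up is not undefined. It has no expected length, however, and the event definition stops at the hospital stay.
- **The discharge rule is narrow.** It covers only a patient who leaves before that day's check and is not a general censoring rule. Indeed, the documents never mention censoring. That working lines are censored at discharge or removal is inferred from the event definition, which is why the plan should say so.
- **The event window might look contradictory**, because telephone calls after discharge ask about function and the Statistical Analysis paragraph repeats no hospital limit. This does not hold up. The Objective section limits the event explicitly, silence elsewhere does not contradict it, and follow-up after discharge is described as being for thrombosis.
- **Buffer losses need not be event-free.** A patient lost after placement still contributes time and possibly a failure. The 99% figure is thus a worst case, and 83% of 212 is the main one.
- **Aim 3 did not set the sample size**, and the confidence interval for the hazard ratio will show the precision achieved. Both are true, and they keep this a matter of correcting one statement.

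**Conclusion.** The point stands as a fault in a stated assumption. The 0.85 is conditional on about 175 functional failures, 83% of 212 catheters (180, or 85%, by Freedman). The plan does not state this condition, and neither its in-hospital event definition nor a median worded as time in the vein supports it. The 175 rests only on the plan's own hazard ratio, alpha, power and allocation.

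Three stronger readings go too far. The 0.85 is not a miscalculation, since it can be reproduced. It does not require that nearly every catheter fail or that nothing be censored early: 17.5% of 212 may never fail, and an assumed censoring median of 39 to 59 days would still be enough. Nor is it shown that Aim 3 is underpowered, because the true failure share is unknown. The illustrative range runs from 0.49 (30% failing) to 0.80 (70% failing), and with a 10-day failure median from 0.62 to 0.79 for 10 to 14 days of observation.

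The consequence is confined to this power statement. Aim 1, the sample size and the reporting of the hazard ratio are unaffected. It should be corrected, and the arithmetic leaves little doubt.

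**What to change.** Replace the Aim 3 power sentence with one based on failures: about 175 functional failures give 0.85 power for a hazard ratio of 1.5 at one-sided 0.05. Follow it with three figures:

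1. the expected share of catheters failing within the in-hospital window set in the Objective section;
2. the number of failures this yields from 212;
3. the resulting power.

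Base the share on time to functional failure rather than dwell, for example from the site's 1,200 BioFlo insertions if failure was recorded there. If no estimate exists, present 0.85 only as conditional on about 175 failures.

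Add one sentence to the Aim 3 analysis saying that discharge with a working line and removal of a working line are treated as censored in the log-rank and Cox analyses.

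The cost is two sentences and a possibly less favourable power figure. Enrolment and the Aim 1 sample size do not change.
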